Exclusion criteria	
 1. No internet access 2. No E-boks access 3. No mobile phone 4. Persons deprived of liberty or under guardianship or curators 5. Dementia, mental alteration or psychiatric disease that can compromise informed consent from the patient and / or adherence to the protocol and the monitoring of the trial 6. Pregnant or breastfeeding women 7. Patient participating in another interventional study during the surveillance period. This is only relevant for studies that might interfere with the intervention. Participation in protocols related only to treatment will not preclude participation in the present study. Cases of doubt will be settled by the protocol committee.
Time of Enrolment	Patient enrolment is always at the time when the patients are informed of the results of their first evaluation scan after treatment induction.
Statistical analysis	The study will be conducted as a randomized phase III study. First analyses will be conducted after 2 years of inclusion. No predefined criteria for termination of the trial has been determined.

Introduction

Lung cancer is a serious disease with a dismal prognosis. The 5-year survival rate of Danish lung cancer patients diagnosed with loco-regional disease ranges from 43% for patients with stage I lung cancer, through 27% for stage II to 21% for patients with stage III disease. Patients with stage IIIb-IV receiving palliative treatment have an even worse outcome, with a 5-year survival of only 4 and 2% estimated in 2015. Of the more than 4500 patients who were diagnosed with lung cancer in Denmark in 2015, 55.6% were in stage IIIb-IV⁹.

According to the national Danish follow-up program for lung cancer, patients are followed with clinical controls and a contrast enhanced CT-scan of the thorax and upper abdomen, every 3 months the first 2-3 years, then every 6 months until 5 years. The purpose of follow-up is to find relapse as soon as possible to increase the probability of curative treatment of the relapse, or if curative treatment is not possible, optimal palliative treatment¹. In case of treatment with palliative intent, patients are usually scanned every 3 months after they have finished treatment to determine the present status of the disease. However, during palliative treatment, patients are often scanned more frequently to evaluate the effect of the ongoing treatment.

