There have been conducted numerous studies of symptom monitoring by patient-reported outcomes (PRO), reviewed recently¹⁰. PRO's are any measurements provided directly from the patients, which give information on aspects of their health status, often relevant to their quality of life. These studies of PRO use for symptom monitoring, have shown improvement in patient-caregiver communication, but have not been able to show improvement in clinical outcome¹⁰. Now, evidence is emerging, showing that a proactive approach of symptom monitoring by use of PRO data, might lead to a better quality of life and improved survival among patients with lung cancer²⁻⁴.

Recently, a study by Denis et al.² suggested, that including weekly patient-reported (PRO) symptom monitoring in the follow-up of lung cancer patients in all stages, could help identify earlier patients with progression or relapse of disease. In their randomized phase III trial, conducted in France, they found a survival benefit of 26% for the PRO intervention group, with a hazard ratio of 0,325 (0,157-0,673). In the study, clinicians were alerted when patients had reported detrimental changes in PRO symptoms, leading to earlier clinical evaluation and CT-scan, if indicated. Earlier detection of progression or relapse allowed for an earlier start of secondary treatment and patients were found in better performance status, leading to improved overall survival.

A significant benefit in quality of life and a survival benefit has also been shown in a study of patients undergoing treatment for cancer, including lung cancer^{3,4}. The patients were randomized between the standard of care vs. regular PRO symptom reporting. When detrimental changes were reported by the patients, they were contacted by the healthcare team for symptom management. The median overall survival was 31,2 months (24,5-39,6) in the PRO group and 26,0 months (22,0-30,9) in the standard of care group, HR=0,83 (0,70-0,99).

Aim

Inspired by the impressive survival benefit found by Denis et. al.², we propose to test, in a Danish setting, whether adding weekly monitoring of patient-reported symptoms, can improve early detection of progressive disease and improve survival for lung cancer patients. The weekly monitoring will be added to the standard evaluation program with clinical control and contrast-enhanced CT of the thorax and upper abdomen.

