Eligible are patients with stage III lung cancer where the treatment intention is palliative and stage IV lung cancer regardless of treatment intent, who have received first-line induction treatment and have stable disease or better response after induction therapy. Maintenance treatment of any kind is allowed during the study period. Patients will be stratified by centre, stage and by main histology; small-cell lung cancer vs. non-small cell lung cancer.

Inclusion Criteria

1. Patients with lung cancer (NSCLC or SCLC) with stage III treated with palliative intention, or stage IV, regardless of treatment intention.
2. 1st line induction treatment* started/completed prior to the current evaluating scan
3. Non-progressive** disease at first CT scan evaluating 1st line induction treatment

4. Diagnosis proved by cytology or histology
5. Age \geq 18 years
6. Performance status (PS) \leq 2
7. First evaluation CT scan performed within four weeks from enrolment
8. The patient has given his/her written informed consent before any specific procedure from protocol

** Induction treatment includes:*

- *Standard doublet chemotherapy*
- *Immunotherapy*
- *Targeted therapy*
- *Palliative radiotherapy*
- *Local treatment of oligometastatic disease, including surgery and stereotactic radiotherapy*
- *Any combination of the above-mentioned treatment modalities. Patients are eligible regardless of whether they at the time of inclusion continue maintenance treatment or not*

*** Patients with stable disease or better response, defined by the treating clinician, are eligible. Patients receiving immunotherapy are eligible if pseudoprogression is suspected based on clinical response and treatment is continued. Patients receiving 1st line "treatment beyond progression" are eligible*

Exclusion Criteria

1. No internet access
2. No E-boks access
3. No mobile phone
4. Persons deprived of liberty or under guardianship or curators
5. Dementia, mental alteration or psychiatric disease that can compromise informed consent from the patient and/or adherence to the protocol and the monitoring of the trial
6. Pregnant or breastfeeding women
7. Patient participating in another interventional study during the surveillance period. This is only relevant for studies that might interfere with the intervention. Participation in protocols related only to treatment will not preclude participation in the present study. Cases of doubt will be settled by the protocol committee.

Time of enrolment

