In the randomised study by Denis et al.² the difference in 1-year survival in control vs. PRO arm was 49% vs. 75% with the significant hazard ratio of 0.33 in their sample of 60 vs. 61 individuals in the two study arms. A power calculation based on a log-rank test for difference in survival with these anticipated survival rates and a follow-up time of 1-year results in for 53 patients in each arm. Given the remarkable difference between the two arms, a more conservative estimate has been calculated for a relative improvement of approximately half this size.

The crude overall 1-year survival in Denmark of 46.2%⁹, but given that patients included in the study are responders of initiated treatment and presumably have better survival, 50 % 1-year overall survival is assumed to be the survival rate in the control arm. A relative improvement of approximately half the size found by Denis et al.² would result in an anticipated survival rate of 63.2%. A difference of this size would require 221 individuals in each group (Alpha 5%, Beta-1 80%).

However, the feasibility study revealed a compliance ratio of 90%, which then requires a total number of 492 patients.

Power calculations were performed in STATA 14.2 using the procedure for two sample survival comparison with the log-rank test.

We aim to collaborate across hospitals to get as many participants as quickly as possible.

Statistics

The study will be conducted as a randomized phase III study. A temporary analysis will be made after 2 years of inclusion and determine whether the study holds enough promise to justify the continuation of patient enrollment. No predefined criteria for termination of the trial have been determined.

Cox proportional hazards regression will be used to estimate the hazard ratios for time to clinical deterioration, time or relapse, and the median time to deterioration.

OS will be compared between the control arms among all randomized subjects using a two-sided, log-rank test. Median OS will be estimated via the Kaplan-Meier method.

Health resources utilized are described in both arms. All hospital costs from the point in time from randomization to 1-year follow up are measured by DRGs (Diagnosis-related groups) and inflated to the price year 2018 using the Danish Hospital PL

(Price and Wage) index. CIs are estimated with bias-corrected non-parametric bootstrapping.

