Cost-effectiveness of the PRO application versus standard monitoring is assessed with the incremental cost-effectiveness ratio (ICER), i.e. the ratio of net health care costs to net QALYs (Quality Adjusted Life Years). For a description of the data collection and the analysis, see appendix.

Statistical analysis plan of the Health-Related Quality of Life data

Health-related quality of life (HRQoL) measures are secondary endpoints in the ProWide trial and will be reported in a scientific paper published separately from the main paper. The primary endpoints of the HRQoL paper are Physical function (QLQ-C30), Pain (QLQ C-30), HADS-anxiety and overall EQ-5D-5L index score.

The statistical analyses were planned before any evaluation of the data collected in the trial was made.

Data collection

The HRQoL questionnaires are sent to the patients via the Danish public mail system (eBoks) every second months. All patients in the trial have access to the system. Non-respondents receive a reminder after one week. Responses delivered > 30 days after the invitation is sent is categorized as “missing”.

Specific endpoints of interest in the HRQoL analysis

The specific HRQoL scales that will be analyzed in the ProWide study are:

1. Physical function (QLQ-C30)

Rationale: Physical function is considered a PRO surrogate marker for performance status which is an important prerequisite for both toleration effect of medical antineoplastic treatment.

2. Pain (QLQ C-30)

Rationale: Pain is sensitive to change toward progression in cancer and a symptom that can be managed with analgesics. The symptom could then be improved through actions that are a result of the intervention.

3. HADS-anxiety

Rationale: The intervention could improve the sense of security in the patients and potentially reduce anxiety.

4. EQ-5D-5L index score

Rationale: The generic score represents an overall self-assessed health status and will be used report the effect of the intervention on the overall health.

The EQ-5D-5L score will be reported both in the main paper as a mean-score comparison between the two groups at six months and also analyzed in the HRQoL paper as described below.

HRQoL hypothesis

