The HRQoL hypothesis is that the natural course of cancer-related symptom deteriorations can be overall reduced through actions taken on the basis continuous symptom monitoring throughout the study period. It is expected that the overall effect is larger than the effect on time to deterioration. This expectation applies to all the HRQoL endpoint.

Statistical analyses

The HRQoL data will be analyzed using a linear mixed model approach as the primary analysis to compare longitudinal data between study arms. Area Under the Curve (AUC) will be used as a confirmatory analysis. These analyses are based on the assumption that the scores can be considered as continuous variables²⁶.

Statistical significance

The mean EQ-5D-5L score will be reported for both study groups at six months in the main paper as the primary HRQoL endpoint.

The four HRQoL endpoints of primary interest will be analyzed and reported in the HRQoL paper.

A p-value of <.05 will be considered statistically significant.

Minimal Important Differences (MID)

MID will be used to report the proportion of patients with improvement, stable or deteriorating symptoms compared to baseline

Physical function (QLQ-C30) and Pain (QLQ C-30): a 50 % reduction of the expected mean deterioration without the intervention from baseline to time of progression is considered the MID. Based on clinical data from lung cancer patient treated in the department of oncology, Regional Hospital West Jutland, Denmark (to be published) the expected mean deterioration from baseline to progression is 10 points. A 50 percent reduction then corresponds to an MID of five point for this study.

HADS-anxiety: A 1.5-point change in the HADS anxiety score is considered an MID²⁷.

EQ-5D-5L index score: A change of 6 points is considered an MID²⁸.

Compliance and missing data

Reasons for missing data will be categorized as; administrative censoring (patients who have not reached the relevant time point at the time of the analysis), withdrawal and missing for participants still in the study. If the reason for non-compliance is death the data will not be categorized as missing.

Compliance is defined as the ratio between the number of responses and expected responses (death and administrative censoring as the reason for non-compliance are excluded at the specific time points).

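### OS is tested without the stage and histology strata used in randomisation, no OS hazard ratio is planned, and the main-paper EQ-5D-5L comparison states no baseline adjustment

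*Combined protocol and SAP*

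**What the plan says.** The Study population section sets the stratification: "Patients will be stratified by centre, stage and by main histology; small-cell lung cancer vs. non-small cell lung cancer".

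The Statistics section gives the primary test: "OS will be compared between the control arms among all randomized subjects using a two-sided, log-rank test". The reference to control arms is evidently a slip for the two trial arms. No strata or covariates are named. The estimate that goes with the test is "Median OS will be estimated via the Kaplan-Meier method". The model that could supply a hazard ratio is assigned to other endpoints: "Cox proportional hazards regression will be used to estimate the hazard ratios for time to clinical deterioration, time or relapse". The only confidence intervals in that section are bootstrap intervals for costs.

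The protocol describes its predecessors by their OS hazard ratios. The Introduction reports the French trial "with a hazard ratio of 0,325 (0,157-0,673") and a second PRO trial at 0.83 (0.70 to 0.99). The Power calculation section takes its target from the French result.

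For EQ-5D-5L, the section on specific HRQoL endpoints says the main paper will report the score "as a mean-score comparison between the two groups at six months". The Statistical significance section gives that result its rank: "The mean EQ-5D-5L score will be reported for both study groups at six months in the main paper as the primary HRQoL endpoint". The Evaluation criteria section has EQ-5D-5L completed at baseline and every two months. The linear mixed model in the HRQoL plan is most naturally read as belonging to the separate HRQoL paper, and its covariates are not specified.

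**The concern.** A trial of 492 patients powered on survival plans a p-value and two medians for its primary endpoint. It plans no relative effect with an interval to set against the hazard ratios it cites. If the model is not named in advance, its covariates can be chosen after the data are seen.

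The other two points concern efficiency. When randomisation is balanced on prognostic factors and the test ignores them, the test tends to be conservative and loses some power. When a six-month score is compared without its baseline, the interval is wider than the collected data allow. This matters more because that comparison is named the main paper's primary HRQoL endpoint.

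**Working it through.** **The plan's sample size.** Inputs from Power calculation: 1-year survival 50% against 63.2%, alpha 5%, power 80%, compliance 90%. HR = ln 0.632 / ln 0.5 = 0.662. Freedman's formula gives 190 events; the mean 1-year death probability is 1 − (0.5 + 0.632)/2 = 0.434, so n = 190/0.434/2 = 219 per arm. A two-proportion formula gives exactly 221. Then 221/0.9 = 245.6, so 246 per arm and 492 in total. The stated figures reproduce with a two-sided, unstratified calculation.

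**What an OS hazard ratio would deliver.** With exponential survival and the 24-month observation time given under Endpoints:
- Deaths = 246 × [(1 − 0.5²) + (1 − 0.632²)] = 246 × (0.750 + 0.601) = 332.
- SE(log HR) = 2/√332 = 0.110.
- 95% CI = 0.662 × exp(±1.96 × 0.110) = 0.53 to 0.82.

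**Cost of leaving out the strata.** The Introduction supplies one prognostic input: "Patients with stage IIIb-IV receiving palliative treatment have an even worse outcome, with a 5-year survival of only 4 and 2% estimated in 2015". Under proportional hazards this gives a stage HR of ln 0.02 / ln 0.04 = 1.2. The rest is assumed: histology HR 1.5, 2.0 or 2.5; 80% stage IV; 15% SCLC; 8 centres with no centre effect; blocks of 4 within centre × stage × histology. Both arms were calibrated to marginal 1-year survival, with 492 patients followed for 24 months, 8,000 simulated trials per power scenario and 16,000 per null. The weaker effect is a marginal HR of 0.735, that is 1-year survival of 0.5^0.735 = 60.1%. Entries are % of trials significant, plain → stratified by stage × histology.

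| Scenario | Histology HR 1.5 | 2.0 | 2.5 |
|---|---|---|---|
| Plan's effect | 95.9 → 96.1 | 96.2 → 96.6 | 96.1 → 97.2 |
| Weaker effect | 81.5 → 81.8 | 80.3 → 81.7 | 79.9 → 83.2 |
| No effect (type I error) | 4.7 → 5.0 | 4.5 → 4.9 | 4.4 → 5.1 |

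Before rounding, the gains are 0.1 / 0.5 / 1.0 points at the plan's effect and 0.4 / 1.4 / 3.4 at the weaker one, with standard errors of 0.1 to 0.3. Moving the SCLC share between 10% and 25% widens these to −0.1 to 1.5 and 0.2 to 4.1.

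A second set of assumptions (85% stage IV, 20% SCLC, stage/histology HRs of 1.3/1.5, 1.5/2.0 and 2.0/2.5, within-stratum treatment HR 0.662, 4,000 trials each) gives, at 24 months, power of 95.8 → 96.2, 95.0 → 95.8 and 93.7 → 96.0. The plain test's type I error is 5.2%, 3.9% and 3.8%.

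**Baseline adjustment of EQ-5D-5L.** With baseline to six-month correlation r, adjustment multiplies the variance by 1 − r² and the interval width by √(1 − r²). The equivalent sample is 1/(1 − r²). The documents give no r, so a range is assumed.

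| r | Variance factor | Width factor | Equivalent sample |
|---|---|---|---|
| 0.3 | 0.91 | 0.954 | 1.10 |
| 0.5 | 0.75 | 0.866 | 1.33 |
| 0.7 | 0.51 | 0.714 | 1.96 |

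These relative gains do not depend on the SD, compliance or the minimal important difference. The number of six-month responders is left open: patients exit the study at progression, and the plan does not say whether questionnaires continue.

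**The case against.** The strongest case against is that the stratified test is close to a preference. The plain log-rank is valid, matches the sample-size method, and at the plan's effect loses about one point of power or less in most scenarios. The larger gains need a weaker treatment effect and a strong histology effect, and neither is in the documents. The remedy also drops centre, a stratification factor. On size this stands, and the point is not a threat to validity. Leaving out centre is deliberate: 8 × 2 × 2 = 32 cells would hold about 15 patients each.

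On OS, it can be said that the health-economic appendix plans a survival analysis for life years, and that Kaplan-Meier curves yield 1-year survival. Neither is a planned between-arm effect with an interval. It is fair, though, that a stratified hazard ratio is conditional, and that the documents do not say whether the cited ones were stratified.

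On EQ-5D-5L, the plan is silent and does not rule out adjustment, so the exact statement is that none is specified. A more serious objection is that baseline questionnaires go out just after inclusion, and randomisation is done at enrolment, in an unblinded trial. Baselines may therefore follow allocation. With an assumed between-arm baseline shift of 0.02, the adjusted difference moves by r × 0.02 = 0.006, 0.010 or 0.014. If the plan's 6-point minimal important difference means 0.06 on the index, the largest of these is 0.014/0.06 = 23% of it. An unadjusted sensitivity analysis would reveal such a shift but would not remove it from the adjusted result.

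**Conclusion.** The concern holds in all three parts and should be corrected. It is about efficiency and reporting; type I error is not inflated.

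The missing OS hazard ratio with its interval is the most important part, and that gap depends on no assumption. Its illustrative size, 0.66 (0.53 to 0.82), rests on the plan's survival rates and exponential survival.

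The unstratified test costs about 0 to 1.5 points of power at the plan's effect and 0.2 to 4.1 at HR 0.735, given assumed stratum shares and histology effects. It is slightly conservative when those effects are moderate or strong.

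The unadjusted EQ-5D-5L contrast forgoes a 9% to 49% reduction in variance for assumed correlations of 0.3 to 0.7. This part concerns the main-paper contrast only, not the separate HRQoL paper.

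**What to change.** **OS.** Make the primary test a log-rank stratified by stage × histology (4 cells, without centre). Report the OS hazard ratio with 95% CI from a Cox model with the same strata, labelled as conditional. Keep the plain log-rank as a sensitivity analysis.

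**EQ-5D-5L.** Adjust the main-paper six-month difference for baseline EQ-5D-5L, stage and histology, in the patients the plan already compares (alive and responding at six months). State how a missing baseline is handled, for example by the mean pooled over both arms, so that no responder is lost. Report the unadjusted difference beside it and say that baselines may have been completed after allocation. If the mixed model is used instead, state how deaths are handled, because the HRQoL plan does not count data absent through death as missing.

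**Cost.** No new data and no change in sample size, but more than one line of SAP text. The primary test would differ slightly from the plain log-rank used for the sample size. At the plan's effect the simulated stratified hazard ratio is 0.650 to 0.660, against 0.663 to 0.666 unstratified. The smallest of the four cells would hold about 492 × 0.20 × 0.15 = 15 patients under the assumed shares.

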A first look on the data before doing the HRQoL analysis will define the cut of point of the analysis according to the following rule. Data obtained from baseline up to 12 months will be analyzed as long as the compliance is at least 50 % in both study arms.

A supplementary analysis will explore potential differences in the HRQoL endpoint between patient with high or low compliance and the dropout rates will be compared between study arms.

Imputation

EORTC QLQ C30/L13

If at least half the items used in a scale are available, the mean scores of these items are imputed to the remaining missing items to calculate the specific scale. If more than half of the items in a scale are missing, this whole scale will be considered missing for the individual patient. This approach (the half rule) is recommended in the EORTC QLQ scoring manual^{5,6}.

Multiple imputation will not be used to adjust for missing data.

Ethics

All patients must give their written consent prior to the study according to local ethical standards and all data will be treated with confidentiality. The study has been approved by the Danish Data Protection Agency. Permissions to withdraw data from DLCR will be obtained.

Both study arms will be offered the CT-scans and clinical evaluations according to standard procedures. In the study presented by Denis et al.², patients in the experimental arm were offered less regular prescheduled CT-scans than control arm, which is not the case in the present study.

Perspectives

The French randomized trial of incorporating PRO data in the follow up of lung cancer patients has shown compelling evidence of a substantial improvement in median and overall survival by using a web-application mediated follow-up⁵. If this Danish adaption of the study shows similar positive results it holds great promise for the future strategy for lung cancer follow-up/response evaluation – and possibly also perspectives for improving follow-up for other cancer patients.

In Denmark there is a unique chance to conduct clinical trials of follow up due to the free and equal access to health care, and the possibility of complete follow up by use of the civil registration number, allowing for linkage between registries, a very low rate of patients lost to follow up and often high completeness of data, leading to good data quality.

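### The main paper's primary HRQoL endpoint, mean EQ-5D-5L at six months, has no stated estimator, no rule for deaths before six months and no stated use of baseline

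*Combined protocol and SAP*

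**What the plan says.** Under *Statistical significance* in the HRQoL analysis plan: "The mean EQ-5D-5L score will be reported for both study groups at six months in the main paper as the primary HRQoL endpoint". Under *Specific endpoints of interest in the HRQoL analysis*, the main-paper analysis is described "as a mean-score comparison between the two groups at six months". That sentence adds that the same score is analysed in the HRQoL paper by the methods that follow it. Those methods, under *Statistical analyses*, begin: "The HRQoL data will be analyzed using a linear mixed model approach as the primary analysis to compare longitudinal data between study arms". An area-under-the-curve analysis is to confirm the result.

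On death, *Compliance and missing data* says: "If the reason for non-compliance is death the data will not be categorized as missing". For the compliance ratio, "death and administrative censoring as the reason for non-compliance are excluded at the specific time points". Under *Data collection*, answers arriving more than 30 days after the invitation count as missing. Under *Imputation*: "Multiple imputation will not be used to adjust for missing data".

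EQ-5D-5L is collected at baseline and every two months (*Evaluation criteria*). *Study period* and the footnote to Table 1 say that patients leave the study at progression. Neither says whether questionnaires continue afterwards, and exit at progression is not among the listed reasons for missing data.

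**The concern.** The trial's primary hypothesis is that the intervention prolongs life. If it does, the two arms have lost different shares of patients by six months, and a mean over the scores available then compares two differently selected groups. The plan gives no value for death, does not say that the target is quality of life while alive, and includes no sensitivity analysis for deaths. The 50% compliance threshold gives no warning, because deaths are removed from its denominator.

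The plan also leaves a simple gain unused. Baseline EQ-5D-5L and intermediate scores exist, and a longitudinal model is planned for the same variable, but the main-paper figure is not tied to either.

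At stake is what the main paper's designated HRQoL result means. Two analysts following the text could report different quantities under the same name.

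**Working it through.** **Inputs from *Power calculation*:** one-year survival 50% (control) and 63.2% (PRO); alpha 5%, power 80%; 221 per arm; 90% compliance; 492 in total. The log-rank test is two-sided (*Statistics*).

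**The plan's own figure.** HR = ln(0.632)/ln(0.50) = 0.662. Freedman events = (1.960 + 0.842)² × [(1 + 0.662)/(1 − 0.662)]² ≈ 190. The mean one-year death probability is (0.500 + 0.368)/2 = 0.434, so 190/0.434/2 ≈ 219 per arm, against 221 stated. Then 221/0.9, rounded up, is 246 per arm, or 492. The sample size reproduces.

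**Deaths by six months.** The plan gives no six-month rate and no hazard shape. With a common Weibull shape k (assumption), S(6) = S(12)^(0.5^k); k = 1 is constant hazard.

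| k | Control dead | PRO dead | Gap (points) |
|---|---|---|---|
| 0.7 | 34.7% | 24.6% | 10.1 |
| 0.8 | 32.8% | 23.2% | 9.7 |
| 1 | 29.3% | 20.5% | 8.8 |
| 1.25 | 25.3% | 17.5% | 7.7 |
| 1.5 | 21.7% | 15.0% | 6.8 |
| 2 | 15.9% | 10.8% | 5.1 |

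At k = 1, √0.50 = 0.707 and √0.632 = 0.795 are alive: about 72 vs 50 deaths among 246 per arm. Control deaths exceed PRO deaths at every shape.

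**Selection bias in the observed mean, two illustrations at k = 1.** Neither set of inputs is in the documents.

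- *Extra survivors score lower.* Suppose everyone who would survive on control also survives on PRO. Extra survivors are then (0.795 − 0.707)/0.795 = 11.1% of PRO survivors. If they score 0.1 to 0.3 lower, the PRO mean falls by 0.011 to 0.033.
- *Normal truncation.* With correlation ρ between health and survival, survivors' mean is raised by ρ × SD × φ(z)/S, where S is the share alive and z cuts off the share dead. The factor φ(z)/S is about 0.486 in control and 0.357 in PRO, a difference of 0.129. For SD 0.15-0.25 and ρ 0.2-0.6, the bias against PRO runs from 0.129 × 0.15 × 0.2 = 0.004 to 0.129 × 0.25 × 0.6 = 0.019.

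Together: 0.004 to 0.033. The plan's MID is 6 points, read here as 0.06 on the index (assumption).

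**Effect of the choice of estimand.** Suppose survivors average 0.75 in both arms (assumption). The survivor difference is 0. With deaths scored 0, the means are 0.75 × 0.707 = 0.530 and 0.75 × 0.795 = 0.596, a difference of 0.066. Survivor means of 0.6 to 0.8 give 0.053 to 0.070, about one MID.

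**The case against.** The text never says that the comparison is confined to surviving responders. The mixed-model sentence is not expressly limited to the HRQoL paper, so the sponsor may intend that model to supply the six-month figure. This stands as far as it goes: the observed-case reading is an inference. It is nevertheless the natural one, because the plan lists the main-paper comparison separately from the later methods. If the model is intended, the plan needs to say so.

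A reader might infer that the plan's survival assumptions imply 29% vs 20% deaths by six months. They do not. Only one-year survival is given, and because patients enter with non-progressive disease, a hazard rising after entry is plausible. That would lower both figures.

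A reader might also take 0.066 as the bias. It is not: with equal survivor means, it is wholly the survival effect on another scale. Equal quality of life among the living is a legitimate answer to a while-alive question. The stated HRQoL hypothesis concerns symptom deterioration, and the plan deliberately separates death from missingness. Survival is captured by the primary endpoint, and survival and utility are combined in the QALYs of sub-study 3. Scoring death as 0 is therefore a choice of estimand and a trade-off, not a correction.

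Finally, HRQoL is secondary, reasons for missing data are to be categorised, and dropout is to be compared between arms. These points limit the consequences. They do not supply a rule for death in the six-month comparison.

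**Conclusion.** The concern holds as a gap in specification. The endpoint has no named estimator, no rule for death and no stated use of baseline. Under the trial's own survival alternative, observed means would come from arms depleted by about 16-35% (control) and 11-25% (PRO) over the shapes examined. The assumption behind this is a common Weibull shape between 0.7 and 2.

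It would go too far to say that the endpoint would turn a survival benefit against the intervention. The illustrated bias of 0.004-0.033 is below the MID, and it runs against PRO only because frailer patients are assumed to die first. Differential exit at progression could push the other way: if earlier detection removes deteriorating PRO patients from the questionnaires sooner, the PRO mean rises.

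Nor would the mixed model alone be a cure. It handles intermittent missing answers and improves precision, but it implicitly extrapolates scores beyond death. The case for change rests on an undefined quantity and a cheap improvement, not on a demonstrated large bias.

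**What to change.** 1. Take the six-month between-arm difference from the planned linear mixed model, with baseline EQ-5D-5L included. Describe it as a comparison in patients while alive, and state that the model does not solve truncation by death.
2. Report per arm the numbers randomised, dead, exited at progression and responding at six months. Label the raw mean descriptive.
3. Add a sensitivity analysis: the six-month mean with deaths set to 0, with a stated method for living non-responders, for example the mixed-model prediction. Without such a method, a mean over all randomised patients cannot be computed. Note that the result partly repeats the OS comparison.
4. State whether questionnaires continue after exit at progression. If they stop, six-month responders are selected further, on being progression-free as well as alive.

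The cost is SAP wording and a small amount of analysis. Items 1 to 3 use baseline, follow-up and mortality data that the trial already plans to collect. Item 4 only needs the existing practice to be stated, but if questionnaires stop at progression, items 1 and 3 rely more on model predictions, and the report should say so.
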